#### *Outcome definitions*

The first outcome will be the 7-day moving average of daily confirmed cases of COVID-19/SARS-CoV-2. The second outcome is the time-varying reproductive number between the current and previous period. The third outcome is the 7-day moving average of the daily number of deaths by COVID-19 in Latin American subnational regions. For the statistical modelling, these averages will be rounded to the nearest integer. We will consider a 7-day lag as the primary lag. We will use the definition of COVID-19 case and death which is valid at any given time in each country.

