#### *Analysis methods*

The primary analysis will use interrupted time series (ITS) for each subnational unit to examine the causal effect of COVID-19 policies on primary outcomes. Interrupted time series is a widely used tool in causal inference that allows comparing trends before and after the introduction of an intervention. The counterfactual outcome is the projection of the trend in the period before the introduction of the intervention into the time period was introduced. The unit of analysis in this study is days, starting from the date of the first case.

The standard model for an ITS regression is as follows

$$(1) Y_t = \beta_0 + \beta_1 time_t + \beta_2 post_t + \beta_3 timepost_t + \beta'_4 X + \mu_t$$

where  $time_t$  is a variable which equals one at the first time point  $t$  and increases by one after each subsequent time point;  $post_t$  is a dummy variable that equals to zero prior to the introduction of the intervention ( $p$ ) and equals one for every time point thereafter;  $timepost_t$  is a variable that equals to zero until time  $p-1$ , and increases by one for each subsequent time point; and  $X$  is a vector of covariates. Coefficient  $\beta_3$  is the coefficient of interest and represents the change in slope after time  $p$ .

The validity of the ITS rests on three assumptions. Assumption 1 states that the expectation of the pre-intervention level and trends would be the same irrespective of whether the sample received the treatment. Assumption 2 states that in the absence of treatment, the outcome of interest would remain unchanged in the post-intervention period. Assumption 3 states that the time trends in the pre and post periods can be expressed as a linear combination of parameters.

Using the potential outcomes framework, the estimated effect of a policy at time  $p$  could be defined as

$$(2) \Delta_t = Y_t(1) - Y_t(0)$$

These difference could also be expressed in terms of two equations

$$(3) Y_t(1) = \alpha_0 + \alpha_1 time_t + \alpha_2 post_t + \alpha_3 timepost_t + \varepsilon_t$$

$$(4) Y_t(0) = \theta_0 + \theta_1 time_t + \theta_2 post_t + \theta_3 timepost_t + \nu_t$$

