where  $Y_t(1)$  is the sequence of outcomes if we treat the unit at time  $p$  and  $Y_t(0)$  the sequence of outcomes in the absence of treatment. Assumption 1 implies no anticipation of treatment, i.e.  $Y_t(1) = Y_t(0)$  for all  $p \leq t_0$ . In other words,  $\alpha_0 = \theta_0$  and  $\alpha_1 = \theta_1$ . Assumption 2 implies that  $\theta_2$  and  $\theta_3$  are equal to zero.

Violations of assumption 1 include anticipation effects when the subjects of the policy can anticipate its initiation and change their behaviour. In the case of the COVID-19 pandemic, the population might, for example, be more likely to adhere to social distancing recommendations during the discussion of a lockdown or take preventive actions when the incidence of cases increases, even before restrictions such as lockdowns are implemented. Violations of assumption 2 include concurrent changes due to history (other concurrent policy, program or societal changes), selection (changes in the composition of the sample at time  $p$ ), instrumentation (changes in the way the outcome is measured) and mis-specification of the functional form of the time trend (in a classical ITS, time is assumed to be a simple linear term). Violations of assumption 3 can occur due to misspecification of the functional form, including failing to account for a delay of the policy to take effect or failing to account for autocorrelation (which can lead to artificially low standard errors). In an epidemic process, cases over time follow a non-linear trajectory (often an exponential, Gompertz or other complex functional forms). Assuming a linear time trend can lead to incorrect counterfactuals and biased effect estimates.

We will examine and handle potential violations to assumptions in the following way:

Assumption 1. We will assess the existence of anticipation effects by visual exploration and examination of the slope prior to the intervention. If there is evidence of potential anticipation effects, we will use a “quasi-myopic” sensitivity analysis, i.e. an analysis that excludes a period of time where anticipation is expected to have happened from the analyses.

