Assumption 2. We will explicitly incorporate co-occurring interventions in a seven-day period as a combination of interventions. We will also adjust for changes in the case definition of COVID-19 cases and deaths for each of the respective outcomes. We will report in the Supplementary Appendix the exact dates considered in the analysis for each country/subnational unit and the interventions included in each intervention period.

Assumption 3. We will introduce flexible spline functions to account for seasonality and long-term trends. We will add a scale parameter, which will be the Pearson statistic divided by the residual degrees of freedom, to account for potential overdispersion (a violation of the Poisson regression assumption). We will test for autocorrelation using the Durbin-Watson tests and visual plots of the autocorrelation function and partial autocorrelation function. If there is evidence of autocorrelation, we will use the Newey-West method to obtain adjusted standard errors.

Therefore, in the final analysis, we will use Poisson regression to model the count data.. The final model is an extension of the regression described in equation 1 with the specifications described above. The model will include each of the interventions (either as single interventions or combinations of), denoted  $j = 1, \dots, J$ . This method allows estimating simultaneously the effect of several interventions. We will consider interventions implemented within a 7-day period as a combination of interventions, following previous studies. This means that the maximum number of combinations of interventions is 52,  $t = 1, \dots, 52$ . We will estimate the effect of the interventions separately when interventions are separated by at least seven consecutive days and for a maximum period of 30 days. The primary analysis will include a 7-day lag to account for the delay in the intervention to be effective, considering the incubation period of SARS-COV2.

$$(5) \ln(Y_t) = \beta_0 + \beta_{1j}time_{tj} + \beta_{2j}post_{tj} + \beta_{3j}timepost_{tj} + \mu_t$$

This model will be run at the municipal level and, therefore, we expect to run 10,000 regressions multiplied by the number of combinations of interventions at each municipal level. Coefficient  $\beta_{3j}$  is the coefficient of interest and represents the change in slope after the intervention  $j$  at period  $t$ .

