In coefficient of interest at a second stage, we will pool the effects for each intervention -or combination of interventions- (i.e. the coefficient of interest  $\beta_{3j}$  from the local level regression) using a random-effects meta-analysis. This meta-analysis will provide information to obtain a pooled effect estimate and a measure of heterogeneity. We will use the  $I^2$  as a measure of heterogeneity.

If the heterogeneity is moderate or high ( $I^2$  higher than 50%), we will carry out a meta-regression to assess whether subnational level determinants can explain the observed heterogeneity. We will analyse the following covariates: (i) Population size, (ii) Population density, (iii) Proportion of population over 60 years old, as a proxy for age structure of the population, (iv) Household density, and (iv) Proportion of population with basic education, as a proxy of socioeconomic status.

The meta-regression has the effect size  $\widehat{\theta}_k$  of a first-stage regression  $k$  as the outcome, covariates  $x_{ik}$ , a fixed effect  $\rho_1 S_a$  for the second-tier level  $a$  (i.e. State or Region) and a random-effect  $\delta_2 N_b$  for the national level  $b$  and a fixed effect  $\rho_2 Y$  for the time of the year (quarterly periods)(equation 6). The equation includes two types of independent errors, where  $\varepsilon_k$  is the sampling error of the effect size and  $\varsigma_k$  is the random-effect error term.

$$(6) \theta_k = \gamma_1 x_{1k} + \dots + \gamma_n x_{nk} + \rho_1 S_a + \delta_2 N_b + \rho_2 Y + \varepsilon_k + \varsigma_k$$

These controls for higher levels of administration and time of the year will allow us to control for constant characteristics at the subnational and national level, as well as changes in the effectiveness throughout the pandemic.

We will carry out the following sensitivity analyses: (1) comparison of effect estimates using a 5-day and 10-day lag; (2) quasi-myopic analyses to control for anticipatory effects (if there is evidence of), and (3) placebo tests evaluating changes at times when no policy was implemented. In the analyses for the number of cases and time-varying R, we will run additional sensitivity analyses estimating the number of SARS-CoV-2 cases corrected by under-ascertainment derived from mortality statistics.

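### Only the slope change is pooled for the reproduction number R, so the pooled result is not a stable measure of how far R fell

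*SAP*

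**What the plan says.** - **Outcome.** SAP, Outcome definitions: "The second outcome is the time-varying reproductive number between the current and previous period". Protocol, Outcomes, counts R among three primary outcomes. Neither document gives an estimator, a smoothing window or the meaning of a period.
- **Model.** SAP, Analysis methods, applies interrupted time series to the primary outcomes without an exception for R. Equations 1 and 5 each contain a level term (beta2) and a slope term (beta3).
- **Effect.** The definition begins "Using the potential outcomes framework, the estimated effect of a policy at time" p, and equation 2 writes it as Y(1) minus Y(0).
- **What is carried forward.** The slope term is singled out under equation 1 and again under equation 5, where it "is the coefficient of interest and represents the change in slope after the intervention". At the second stage, "we will pool the effects for each intervention -or combination of interventions", and the text names beta3 as the quantity pooled. I-squared and the meta-regression follow from it. Beta2 is not mentioned at that stage.
- **Lag and window.** "The primary analysis will include a 7-day lag to account for the delay in the intervention to be effective". Effects are estimated separately when interventions are "separated by at least seven consecutive days and for a maximum period of 30 days".
- **Fit to R.** Protocol, Statistical analysis, ties the Poisson model to two outcomes and describes the pooling in terms of cases and deaths only, although three outcomes are listed. This suggests that the analysis was not adapted to R.

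**The concern.** For log cases or deaths, the slope is the growth rate, and a policy that slows transmission bends the line. Beta3 is then a natural effect measure. R is already a measure of growth. If a policy cuts R abruptly and R stays down, ln R shifts by ln(R1/R0) and runs parallel to its old path. The effect is in beta2, and beta3 is zero if R is unsmoothed and the shift falls on the modelled day. A non-zero beta3 can then come from onset earlier or later than the assumed lag, from gradual phase-in, or from a smoothing window that spreads the step over several days.

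At stake is one of three primary outcomes. The pooled R result could look weak, or move with the lag chosen, for a policy that worked. It could also disagree with the case result because of the coefficient and not the policy. The second and third aims (local heterogeneity and its explanation) would, for R, compare units on a quantity that mixes size of effect with timing.

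**Working it through.** The documents give no effect size or power figure for R, so there is no stated figure to reproduce. The check shows what beta3 returns when the true fall is known.

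**From the SAP:** the coding of the time, post and timepost terms, the lags of 5, 7 and 10 days, and the 30-day maximum.

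**Assumed, not in the documents:** daily ln R as the response, R from 1.6 to 1.1 (ratio 0.688), serial interval mean 5 and SD 2.5 days, trailing 7-day window for R, an isolated fit to 30 days before and 30 after the lagged change point, linear trend, no noise.

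**Formulas.** ln R = b0 + b1·time + b2·post + b3·timepost. The contrast is exp(mean of b2 + k·b3 over k = 1 to 30). The mean of k is 15.5, so this is exp(b2 + 15.5·b3).

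**Step 1: one series, three planned lags.** R steps down 7 days after enforcement. Lag days are excluded from the pre-period.

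| Lag | beta3 | 15.5·beta3 | ln contrast | beta2 by subtraction | Share in beta3 | Contrast (true) |
|---|---|---|---|---|---|---|
| 5 | -0.0099 | -0.153 | -0.313 | -0.160 | 49% | 0.731 (0.705) |
| 7 | -0.0061 | -0.095 | -0.338 | -0.244 | 28% | 0.713 (0.688) |
| 10 | -0.0019 | -0.029 | -0.364 | -0.334 | 8% | 0.695 (0.688) |

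The data and the policy are the same throughout, yet the part that the SAP would pool goes from about half of the fall to under a tenth. If lag days are kept as pre-period, beta3 at lag 10 is +0.0003. Beta3 for cases in the same series lies between about -0.08 and -0.067, so it keeps its sign and most of its size.

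**Step 2: two units, 7-day lag.** R falls 50% from day 5 in unit A and 31% from day 10 in unit B.

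- A: beta3 = -0.0063 (-0.0044 with lag days kept), contrast 0.518 (true 0.500).
- B: beta3 = -0.0115, contrast 0.740 (true 0.714, since 27 of the 30 days are affected: 0.688^(27/30)).

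The smaller fall has a beta3 that is 0.0115/0.0063 = 1.8 times as large. Over ratios 0.50 to 0.95 and onsets on days 5 to 10, beta3 puts 14% of 1,620 unit pairs in the wrong order (17% with lag days kept). The contrast misorders 0.2% (0%).

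**Step 3: how much sits in beta2.**

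- Step on the modelled day, unsmoothed: all of it, and beta3 = 0.
- Same timing, 7-day window, 30 days: 28% in beta3 (Step 1), so 72% in beta2. For falls of 2.0 to 0.8, 1.5 to 0.9 and 1.5 to 1.2, with the log of a 7-day mean of R, the beta2 share is 56%, 63% and 67%.
- Phase-in over 7 or 14 days: about 44% or 14%. Over 21 or 30 days beta2 is slightly positive (+0.015, +0.026) and the fall is in beta3.
- For the same three falls, onset 3 days late gives 19% to 35%, and a 14-day window gives 19% to 34%.

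The split therefore depends on features other than the size of the fall.

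**The case against.** **Beta3 does carry information.** This stands. At a fixed onset and smoothing, a larger fall gives a larger beta3: with the 7-day window and an on-time step, falls from 1.6 to 1.4, 1.1 and 0.8 give -0.002, -0.006 and -0.012. A slow fall belongs largely in beta3. A reader might infer that a fall in R always sits mainly in beta2, or that beta3 for R is meaningless. Step 3 supports neither.

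**R is not fully defined.** This stands and limits confidence. The outcome definition can be read as a comparison between periods and not as a daily series. Both beta3 and the contrast would then need rethinking. The calculations also use an isolated window, while the SAP uses data to the end of 2020, several interventions in one model, and splines.

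**Equations 2 to 4 do not single out R.** Correct. With the SAP's assumptions they give an effect of alpha2 + alpha3·timepost for any outcome, so dropping alpha2 is not peculiar to R. The case for R rests on what R measures.

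**Sensitivity analyses cover this.** Only in part. The "comparison of effect estimates using a 5-day and 10-day lag" would show the instability. Neither it, the quasi-myopic analysis nor the placebo tests brings in beta2.

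**Harm to the heterogeneity analysis.** A reader might infer that timing differences alone would trigger the meta-regression. The documents do not support that: they give no between-unit spread of onset, and lags of 5 and 10 days are sensitivity settings. With onset on days 5 to 10, one true effect in every unit and noise SD 0.1 or 0.2 on ln R, I-squared for beta3 was 23% or 11% (45% or 22% with lag days kept), all under the 50% gate. With onset on days 6 to 8, misordering falls from 14% to 7%.

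**Conclusion.** The point holds in limited form and should be fixed before analysis. The SAP pools only beta3 for R, and beta3 alone is not a stable measure of how far R fell, because its size, and sometimes its sign, also depends on onset timing, phase-in, smoothing and window length. In the illustration, moving between the SAP's own lags changes beta3 about fivefold (0.0099/0.0019), while the contrast changes by about 5% (0.731/0.695).

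These magnitudes rest on an assumed daily ln R series, smoothing window, pre-period and linear trend. The harm to I-squared and meta-regression cannot be sized from the documents. Cases and deaths are not affected. Confidence is moderate.

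**What to change.** For R only:

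1. State the estimator, what a period means, and the first-stage model (for example unrounded ln R as a continuous response, not Poisson counts).
2. At the second stage, pool a pre-specified contrast of both coefficients. One option is the mean of beta2 + k·beta3 over the post-lag days, up to the SAP's 30-day maximum or the next intervention, with its variance from the joint covariance.
3. Report pooled beta2 and beta3 beside it.
4. Do not count the lag days as pre-period.
5. Keep the 5- and 10-day lag and quasi-myopic analyses. The SAP itself notes that people may "be more likely to adhere to social distancing recommendations during the discussion of a lockdown", and early onset biases the contrast too: a step 7 days before enforcement gives 1.16 against 0.688, and 0.688 again once those 7 days are also excluded.

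Keep beta3 for cases and deaths. Minimum-day rules, any dropping of smoothing-window days, and the trend for R (to be reconciled with the planned splines) are for the sponsor to choose.

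**Cost.** SAP wording and code only, since beta2, beta3 and their covariance come from the same fit. Excluding lag days widens the standard error of the ln contrast. With 30 post-lag days, it is 0.68 times the noise SD if the lag days are kept among 30 pre-days and 1.09 if 7 of those are lost, but 0.82 with 30 usable pre-days and 0.45 with 60. Some closely spaced interventions become non-estimable for R: if the next intervention's lag days are also excluded, a spacing of s days leaves s - 7 post-lag days, so 7 to 13 days apart leaves 0 to 6. The documents do not give the spacing, so the number lost is unknown and should be reported.

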In this study, we aim, first, to estimate the effectiveness of nonpharmaceutical interventions on SARS-COV2 transmission and COVID-19 mortality in Latin America; second, to examine the effect heterogeneity of transmission and mortality at the local level. Third, assuming we find evidence of moderate to substantial heterogeneity at the local level, we aim to explore potential explanations for this heterogeneity. We will use an interrupted time series method to estimate their effects in each local government, and random effects meta-analysis and meta-regression to obtain pooled effects, heterogeneity estimates and potential explanations.

Methods

Design and setting

The study is a natural experiment where we exploit the variation in the temporal and spatial implementation of policy interventions, aimed to reduce the spread and mortality of COVID-19 in Latin America. The unit of analysis are local governments, i.e. third-tier administrative levels such as municipalities, districts or cantons.

We will include all countries fulfilling the following eligibility criteria: (1) Spanish or Portuguese speaking countries in Latin America, and (2) availability of open data at the subnational level for either of the outcomes. Appendix I presents the eligible countries, the exclusion criteria and the sources of data for each excluded country. To date, eligible countries are Argentina, Brazil, Chile, Colombia, Costa Rica, Guatemala, Mexico, Paraguay, and Peru. These countries represent 80.9%

of the population in Latin America, and the vast majority of SARS-CoV-2 cases and COVID-19 deaths.

Interventions

We will examine the impact of several interventions to tackle the COVID-19 pandemic. These interventions include (i) policies aimed at reducing viral transmission, (ii) policies aimed at increasing the capacity of the health system's response, and (iii) policies aimed at mitigating the negative consequences of the epidemic and potential adverse effects of interventions. We will use the PoliMap taxonomy to categorise the examined policies.¹⁸ Table 1 describes the policy interventions in each policy domain included in the study.

Table 1. Policy interventions included in the study

Domain	Policy interventions

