Viral spread (for both outcomes)	Total lockdown Partial lockdown (geographical, step-wise/graduated response) Curfew School closure Closure of shopping malls, gyms, churches, parks Remote work Restrictions to national/subnational mobility Prohibition of mass gatherings
Health systems response (for COVID-19 deaths outcome)	Interventions to increase testing capacity Interventions to increase the number of ICU/critical beds
Mitigation strategies (for both outcomes)	Direct social assistance (in-kind/cash) Cash transfer Withdrawal of pension funds

Comparator

In an interrupted time series analysis, the comparator is a counterfactual outcome defined as the projection of the pre-intervention trend to simulate what would have happened if the policy had not occurred (see Statistical Analysis Plan for definitions).

Outcomes

We will assess three primary outcomes. The first outcome will be the 7-day moving average of daily confirmed cases of COVID-19/SARS-CoV-2. The second outcome is the time-varying reproductive number between the current and previous period.¹⁹ The third outcome is the 7-day moving average of the daily number of deaths by COVID-19 in Latin American subnational regions. For the statistical modelling, these averages will be rounded to the nearest integer. We will consider a 7-day lag as the primary lag. Details on sensitivity analyses can be found in the Statistical Analysis Plan.

We define the outcomes following the official national sources definitions, as each country applies its criteria to define the occurrences and the deaths caused by COVID-19. It is important to note that those criteria are not always clearly stated, but all subnational units are under the same measure at each time.

Data sources

We will obtain COVID-19 cases and deaths data, as well as the covariates, on official government sources, such as the Ministry of Health and Ministry of Science and Technology (see Supplementary Appendix Table S2). The intervention information will come from legal documents, official statements, and quantitative accounts from trustable sources.

Covariates

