The first model at the local level does not include covariates (see below). The second model (i.e. the meta-analysis), we will examine the change in heterogeneity after adjusting for several covariates at the local level. Local level covariates include projected population size in 2020, demographic density, age-structure of the population, household density and socioeconomic status. We will use data from official sources of information, primarily the latest national population census in each included country.

Statistical analysis

The Statistical Analysis Plan provides details on the modelling assumptions. We will use an interrupted time series design, where each local government acts as its own control.^{20,21} The main

strength of this design is its capacity to distinguish the effect of the intervention from secular change.²² We will use a Poisson regression to model the count data (for both outcomes) and accounting for overdispersion and secular trends.²³ A full discussion on potential biases and violations of assumptions can be found in the Statistical Analysis Plan.

In a second stage, we will use random effects meta analysis to pool the effect estimates for each intervention or combination of interventions. This analysis informs whether any implemented intervention was effective to reduce COVID-19 cases and deaths and the degree of heterogeneity between the effects at the local level. If we observe high levels of heterogeneity (defined as higher than 50%), we will also use standard meta-regression techniques to assess whether local level determinants (see *Covariates*) can explain the observed heterogeneity.

We will build the models and test the analytical strategy using publicly available data on COVID-19 cases and deaths from Finland and Sweden from January 1 to March 31.

References

2. United Nations Department of Economic and Social Affairs. World Social Report 2020: Inequality in a rapidly changing world. New York, United States: United Nations; 2020.
3. World Health Organization. Report of the WHO-China Joint Mission on Coronavirus Disease 2019 (COVID-19)2020. <https://www.who.int/docs/default-source/coronaviruse/who-china-joint-mission-on-covid-19-final-report.pdf> (accessed March 26, 2020).

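### Slope changes are pooled by policy label alone, so region-wide and municipality-only enforcement, which have different counterfactuals for a transmissible infection, can be averaged into one effect

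*SAP*

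**What the plan says.** The Protocol (Comparator) defines the comparator as "the projection of the pre-intervention trend to simulate what would have happened if the policy had not occurred". The SAP (Analysis methods) repeats this: "The counterfactual outcome is the projection of the trend in the period before the introduction of the intervention". Its potential outcomes are indexed by the unit's own treatment only, since Y(1) "is the sequence of outcomes if we treat the unit at time" p. The Protocol (Statistical analysis) describes a design "where each local government acts as its own control".

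The design is also meant to "exploit the variation in the temporal and spatial implementation of policy interventions" (Protocol, Design and setting), so policies differ by place as well as date. Table 1 lists "Partial lockdown (geographical, step-wise/graduated response") apart from total lockdown. Another label covers mobility restrictions at national and subnational level together. The remaining labels say nothing about geographic reach.

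At the second stage the SAP says "we will pool the effects for each intervention -or combination of interventions- (i.e. the coefficient of interest" from each local regression), with no split by who enforced the policy or over what area. A meta-regression (equation 6) follows only if I² exceeds 50%. It has five covariates (population size, population density, share over 60, household density, basic education), a state or region fixed effect, a country random effect and a quarter fixed effect. Transmission between units does not appear among the listed assumption violations, their handling, the covariates or the sensitivity analyses.

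**The concern.** When a policy is enforced across a region, the municipality and its surroundings change together, and the projected trend stands for no policy in the area. When it is enforced in one municipality only, infections keep arriving from neighbours whose epidemic continues, and the projected trend stands for no policy here with the neighbours as they were. The same cut in local transmission then gives two different values of β3j.

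Three results are exposed:

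- **The pooled effect (first aim)** becomes an average whose value depends on how many municipalities fall into each situation.
- **A reading of one policy against another** can reflect reach rather than effectiveness, if labels differ in that mix.
- **The size and density coefficients (third aim)** can pick up importation or enforcement level, if either is related to size.

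**Working it through.** The documents state no effect size, power or mixing figure, so there is no figure of the plan's to reproduce. The check asks how far β3j moves under stated assumptions.

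**Inputs from the SAP.** 7-day average, 7-day lag, effect window of at most 30 days, log-linear Poisson segmented regression (equation 5).

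**Assumed inputs.** R = 1.4; mean generation interval 6 days; mean infection-to-report delay 9 days; the policy cuts residents' transmission by 40%; a share w of a municipality's infections comes from outside; 30 days before the break. Splines are omitted.

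**Model.** With g the generation-interval weights, I local infections and N infections in the surrounding region:

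- I(t) = R·c(t)·[(1 − w)·Σ g(s)·I(t − s) + w·Σ g(s)·N(t − s)]
- N(t) = R·c′(t)·Σ g(s)·N(t − s)

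After the policy, c = 0.6. For region-wide enforcement c′ = 0.6 too; for municipality-only enforcement c′ = 1. The closed-area reproduction number falls to 1.4 × 0.6 = 0.84, but with c′ = 1 the outside term keeps growing at R = 1.4 and pulls local growth back towards the regional rate.

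**Step 1: dilution over 30 days.** Region-wide β3 = −0.076 per day. Municipality-only:

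| Outside share w | Ratio to region-wide | β3 (= −0.076 × ratio) |
|---|---|---|
| 5% | 85% | −0.065 |
| 10% | 73% | −0.055 |
| 20% | 55% | −0.042 |
| 30% | 43% | −0.033 |
| 40% | 34% | −0.026 |

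For w from 5% to 30%, the ratio is 96% to 77% with 14 post-policy days and 98% to 91% with 7. With R = 1.2 and 30 days it is 87% to 40% (w from 5% to 40%). A second build of the model gave 83% to 32% over 30 days and 98% to 87% over 7 days (w from 5% to 40%).

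**Step 2: dependence on model structure.** If the policy does not cut residents' exposure to imported infection, w = 5% gives 73% instead of 85%; without the reporting delay as well, 45%. A model with a 5-day generation interval, no delay and imports not cut gives ratios of −0.05 to 0.46 at 5% importation (R 1.3 to 2.0, cuts of 30% to 50%). The direction is stable; the size is not.

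**Step 3: the pooled effect.** With a share p of effects region-wide, pooled β3 = p·(−0.076) + (1 − p)·(−0.044). Here −0.044 is the municipal mean when w averages 20% and varies between units.

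- p = 0.75: −0.057 − 0.011 = −0.068
- p = 0.50: −0.038 − 0.022 = −0.060
- p = 0.25: −0.019 − 0.033 = −0.052

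The local cut is 40% in every case; only the mix differs.

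**Step 4: ranking of policies.** In the model without delay, at R = 1.6, a region-wide policy with a 30% cut gives −0.058. A municipality-only policy with a 40% cut gives −0.083 at zero importation, −0.044 at 2% and −0.020 at 5%. The weaker policy then appears the stronger.

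**Step 5: the population-size coefficient.** The true policy effect is identical everywhere.

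| Situation | Gradient per SD of log population |
|---|---|
| w averages 20%, falls 8 points per SD; all municipal | −0.0092 |
| Same, half region-wide and half municipal | −0.0047 |
| Same, all region-wide | 0 |
| w constant at 20%, half and half, level unrelated to size | 0.0000 |
| w constant at 20%, level correlated with size (example) | +0.008 |

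The second build gave −0.0101, −0.0049 and 0 for the first three rows. When w falls with size, spillover causes the gradient, and mixing in region-wide policies roughly halves it. Mixing itself produces a gradient only in the last row.

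**Step 6: does a level term help?** When level is correlated with size (w = 20%, R = 1.6, state fixed effects), the gradient is +0.0319 per log10 population without the term. With level and its interaction with size, it is −0.0002 among region-wide policies and +0.0009 extra among municipal ones. When w falls with size, the term brings the region-wide gradient to about 0 (+0.0001), but the municipal gradient remains in full.

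**The case against.** A reader might infer that pooling creates a false population-size gradient. The documents do not support that. They give no link between size and importation, or between size and enforcement level, and Step 5 shows that under the first link pooling dilutes the gradient.

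A reader might also infer that policy comparisons are biased outright. That needs labels to differ in their mix of enforcement levels and importation to be above zero, and neither is documented. Total and geographical lockdown are already separate labels, so splitting within labels does not repair that comparison, and no aim names it.

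The effect of a municipal policy with neighbours as they were is a legitimate quantity. Random-effects pooling allows true effects to differ, and heterogeneity is the second aim. This stands, but the plan neither names that quantity nor lets a reader tell the two kinds apart.

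The state, country and quarter terms may absorb some of the difference, and a shift from national to local enforcement over the year could partly fall into the quarter effect. However, they enter only equation 6, not the pooled estimate, and cannot separate levels within one state and quarter.

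The 30-day figures are the plan's maximum window. Breaks may be seven days apart, where dilution is small. The first-stage splines, the reproduction-number outcome and the full equation 6 were not simulated. These limits stand and make the sizes illustrative.

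**Conclusion.** The point holds in this form: the plan does not define the counterfactual for neighbouring areas or record enforcement level, and pooling by label alone can mix two estimands. The omission follows from the documents; its size does not. Under the assumptions above, municipality-only enforcement yields about 85% to 34% of the region-wide slope change over 30 days, and 98% to 91% over 7 days at outside shares up to 30%. Other model structures give stronger dilution. Distorted policy comparisons and a confounded size or density coefficient are possible consequences, each resting on a condition that the documents leave open. This should be changed, at medium confidence; it does not invalidate the design.

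**What to change.** In SAP, Analysis methods (second stage):

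1. Code for each policy the enforcement level (national, state, municipal) and the share of the surrounding state's population under the same policy at the break date.
2. Report the pooled β3j by level beside the overall estimate, with the mix of levels for each label.
3. Add level or coverage share, and its interaction with population size and density, to equation 6. Interpret size and density effects mainly among region-wide policies, because the term isolates the municipal gradient but does not remove it.

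In Protocol, Comparator, state that for municipal policies the counterfactual holds neighbours' policies as they were. Compare labels, such as total and geographical lockdown, only at similar coverage or with this caveat.

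I would not extend the seven-day rule to count adjoining municipalities' policies as co-occurring. That would fragment the combinations and would need adjacency data for about 10,000 units, which the plan does not mention.

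**Cost.** SAP wording and one or two derived variables. Interventions and dates per country or subnational unit are already to be reported, and population size is already a covariate, but level must be coded from the policy records. Level-specific estimates rest on fewer municipalities and have wider intervals.
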